6.1.1 Screening Assessments

Patients identified by the study sites as potential study participants will undergo the following screening assessments:

- Inclusion and exclusion criteria, including written informed consent for participation in the study.
- Demography, medical history (including details concerning allergic tendencies), review of previous therapy.

NOTE: If the period between screening and treatment is more than 3 months, informed consent will be re-reviewed and confirmed prior to treatment, and details of the review process will be recorded in the patient chart and indicated in the CRF by the investigator. Also inclusion/exclusion criteria will be confirmed prior to treatment.

6.1.2 Assessments in Subjects Undergoing On-demand Treatment of Bleeding

Subjects presenting to the study site for an acute bleeding episode will undergo a 30-day observation and follow-up period as outlined below. Throughout the study, subjects may undergo more than one 30-day observation and follow-up periods for treatment of additional bleeding episodes as required until the close of the study. At the end of their study participation, patients will be asked to return for a final Study Completion Visit.

For information on the dose calculation and a definition of minor and major bleeding, see Section 5.4.2. The flow chart of assessments for on-demand treatment is provided on page xxi.

NOTE: All adverse events (AEs, see Section 7.4), including thromboembolic events and early signs of allergic or hypersensitivity reactions, occurring between the start of the first *Octafibrin* infusion and the end of each 30-day observation and follow-up period will be recorded. Concomitant medications will also be recorded throughout each 30-day observation and follow-up period. Administered doses of *Octafibrin* will be recorded for every infusion, including dates, times, and batch numbers.

All SAEs occurring after the first IMP infusion will be documented and reported for a patient throughout the duration of the patient's participation in the study or as required to meet local regulations. Also, any concomitant medications used to treat an SAE will be recorded.

6.1.2.1 Day 1 (first day of treatment)

For subjects requiring on-demand treatment, Day 1 is the day they present for treatment of an acute bleeding episode.

Pre-infusion assessments

The following assessments will be performed before the first infusion of *Octafibrin* for each bleeding episode:

- Medical history (including details of any non-study bleeding episodes and therapy), and prior/concomitant medication.
- Characterisation of bleeding episode.
- Vital signs.
- Physical examination.
- Height and weight.
- Blood draw for:
 - fibrinogen plasma level (local lab–activity; central lab–antigen and activity; within 30 minutes before infusion)
 - MCF (within 30 minutes before infusion).
 - safety lab (local-haematology and clinical chemistry)
 - thrombogenicity
 - immunogenicity retention plasma and serum samples for potential retesting (within 30 minutes before infusion).
- Urine (dip stick) or blood pregnancy test for all female subjects of childbearing potential.

NOTE: If the period between screening and treatment is more than 3 months, informed consent will be re-reviewed and confirmed prior to treatment, and details of the review process will be recorded in the patient chart and indicated in the CRF by the investigator. Also, inclusion/exclusion criteria, will be confirmed prior to treatment.

First infusion of Octafibrin

After the pre-infusion assessments, subjects will receive the first infusion of *Octafibrin* for treatment of bleeding (see Section 5.4).

Post-infusion assessments

On Day 1, the following post-infusion assessments will be performed:

1 hour (± 15 minutes) after the end of infusion:

- Vital signs.
- Blood draw for:
 - fibrinogen plasma level (local lab–activity; central lab–antigen and activity)
 - MCF
 - safety lab (local-haematology and clinical chemistry)
 - thrombogenicity
 - retention plasma samples for potential retesting.

3 hours (± 15 minutes) after the end of infusion:

- Vital signs.
- Blood draw for:
 - fibrinogen plasma level (central lab-antigen and activity)
 - safety lab (local-haematology and clinical chemistry)
 - thrombogenicity
 - retention plasma samples for potential retesting.
- AEs and concomitant medications.

NOTE: If, in the investigator's judgement, the infusion of *Octafibrin* administered on Day 1 is deemed the only infusion needed for treatment of the subject's bleeding event, the subject will need to reach the end of the treatment observation period, where the "24 hours (i.e., 1 day) after the last infusion" assessments should be performed.

6.1.2.2 All Study Days after Day 1 (Treatment Observation Period)

Each subject's **treatment observation period** is defined according to the severity of the event and will last at least **3 days for minor and 7 days for major bleeding episodes**. If the patient requires multiple infusions, the actual treatment duration will be determined by the investigator based on his/her judgement of the subject's condition, and the treatment observation period will last until 24 hours after the last infusion.

Daily assessments (for at least 3 days for minor bleeding or 7 days for major bleeding)

- Blood draw for:
 - fibrinogen plasma level (local lab–activity; central lab–antigen and activity): Based on local lab results, the investigator will determine whether additional infusions of *Octafibrin* are needed.
 - safety lab (local–haematology)
 - retention plasma samples for potential retesting.
- AEs and concomitant medications.

Octafibrin infusion, as required

After these daily assessments, dosing should occur as required depending on the actual and target plasma levels based on the following criteria:

- If the actual fibrinogen plasma level is below the accepted lower limit of the target fibrinogen plasma level (80 mg/dL for minor bleeding, 130 mg/dL for major bleeding; see Section 5.4), the subject should receive another infusion of *Octafibrin*.
- If the fibrinogen plasma level is greater than or equal to the accepted lower limit of the target fibrinogen plasma level, *Octafibrin* **should not** be administered on that day.

Pre- and post-infusion assessments

If the subject receives an infusion of *Octafibrin*, the following pre- and post-infusion assessments will be performed:

Pre-infusion assessments:

- Blood draw for (within 30 minutes before infusion):
 - fibrinogen plasma level (local lab-activity; central lab-antigen and activity)
 - retention plasma samples for potential retesting.

1 hour (\pm 15 minutes) after the end of each infusion:

- Vital signs.
- Blood draw for:
 - fibringen plasma level (local lab-activity; central lab-antigen and activity)
 - safety lab (local-haematology and clinical chemistry)
 - thrombogenicity
 - retention plasma samples for potential retesting.

NOTE: If, in the investigator's judgement, there are no additional infusions of *Octafibrin* needed to treat the bleeding event, the subject will need to reach the end of the treatment observation period, where the "24 hours (i.e., 1 day) after the last infusion" assessments should be performed.

6.1.2.3 Last Infusion or End of the Observation Period (whichever comes last)

If a patient requires multiple infusions for a bleeding event as defined by the investigator based on his/her judgement of the subject's condition, or the subject comes to the end of the observation period (whichever comes last), the following assessments will be performed:

Pre-infusion assessments

The following assessments will be performed prior to the last infusion of *Octafibrin* if multiple infusions are needed:

- Blood draw for (within 30 minutes before infusion):
 - fibrinogen plasma level (local lab-activity; central lab-antigen and activity)
 - retention plasma samples for potential retesting.

Last infusion of Octafibrin

Following the pre-infusion assessments, subjects will receive their last infusion of *Octafibrin* depending on the actual and target plasma levels (see Section 5.4).

Post-infusion assessments

On the Day of Last Infusion, post-infusion assessments will be as follows:

1 hour (± 15 minutes) after the end of last infusion:

- Vital signs.
- Blood draw for:
 - fibrinogen plasma level (local lab–activity; central lab–antigen and activity)
 - MCF
 - safety lab (local-haematology and clinical chemistry)
 - thrombogenicity
 - retention plasma samples for potential retesting.

3 hours (± 15 minutes) after the end of last infusion:

- Vital signs.
- Blood draw for:
 - fibrinogen plasma level (central lab–antigen and activity)
 - safety lab (local-haematology and clinical chemistry)
 - thrombogenicity
 - retention plasma samples for potential retesting.

24 hours (i.e., 1 day) after the last infusion or at the end of the treatment observation period (whichever comes last)

- Vital signs.
- Physical examination.
- Blood draw for:
 - fibrinogen plasma levels (central lab–antigen and activity)
 - safety lab (local-haematology and clinical chemistry)
 - thrombogenicity
 - retention plasma samples for potential retesting.
- Final assessment of haemostatic efficacy by the investigator with respect to the adequacy of stopping an acute bleed. The assessment is to include the entire period from the start of the first infusion until 24 hours (i.e., 1 day) after the last infusion and includes the clinical condition of the subject, laboratory values such as haematocrit and haemoglobin, and any additional haemostatic treatments (see Section 7.2.1).
- AEs and concomitant medications.

6.1.2.4 Day 14 (13 Days after the First Infusion)

On Day 14 (\pm 2 days), the following assessments will be performed:

- Blood draw for:
 - immunogenicity
 - retention plasma samples for potential retesting.
- AEs and concomitant medications.

6.1.2.5 Day 30 (29 Days after the First Infusion)—Final Examination

On Day 30 (± 1 week), the following assessments will be performed:

- Physical examination.
- Blood draw for:
 - immunogenicity
 - retention plasma samples for potential retesting.
- AEs and concomitant medications.

The Day 30 assessment concludes the series of observations by bleeding episode. No further study-related assessments will be performed, unless safety concerns (e.g., ongoing AEs) require follow-up.

Subjects returning to the study site for another acute bleeding episode within the study observation period will again undergo the same Day 1 to Day 30 assessments as outlined in Section 6.1.2.1 through Section 6.1.2.5. At the end of the study duration, all subjects will be asked to return for a Study Completion Visit as summarised in Section 6.1.4.

If a patient experiences another bleeding event between Day 14 and Day 30, this will be treated as a new bleeding event, provided that it is not directly related to the prior event. In this case, the Day 30 evaluations will be postponed until 30 days after the start of the new bleeding episode.

Any additional bleeding episodes will be documented in the same way as the first bleeding episode. These will not be used for the analysis of the primary endpoint, but they will be analysed as a secondary endpoint.

6.1.3 Assessments in Subjects Undergoing Surgical Prophylaxis

Subjects enrolled for elective surgery will undergo a treatment and assessment cycle as outlined in Section 6.1.3.1 through Section 6.1.3.3. *Octafibrin* will be given prior to surgery as well as during and after surgery based on the physician's judgement, the patient's history, and the severity of the procedure. Subjects enrolled for elective surgery will be treated (as required) and assessed from Day 1 (i.e., the day of surgery) to the Last Post-Operative Day. The Last Post-Operative Day is either post-operative day 3 for minor and post-operative day 7 for major surgery or the day of the last post-operative infusion, whichever comes last.

For information on the dose calculation and a definition of minor and major surgery, see Section 5.4.

The flow chart of assessments for surgical prophylaxis is provided on page xxii.

Definitions of Pre-, Intra-, and Post-operative

- **Pre-operative** refers to the time period covering the last 12 hours before the start of surgery.
- **Intra-operative** is defined as the time from the start of surgery to the end of surgery, i.e., the time of completion of the last suture.
- **Post-operative** refers to the time from the end of surgery to the Last Post-Operative Day.

Determination of Fibrinogen Plasma Levels in Surgical Prophylaxis

Fibrinogen plasma levels will be documented immediately (≤30 minutes) before and after each pre-, intra-, or post-operative injection of *Octafibrin*.

Estimation of Blood Loss

Prior to surgery, the surgeon will provide written estimates of the following:

- Volume (mL) of average expected blood loss for the planned surgical procedure, as it would be expected for the same procedure in a subject with normal haemostasis, of the same sex, age, and stature.
- Volume (mL) of **maximal expected blood loss** for the planned surgical procedure as it would be expected for the same procedure in a subject with normal haemostasis, of the same sex, age, and stature.

Following surgery, the **actual blood loss** will be estimated by the surgeon.

NOTE: All adverse events (AEs), including thromboembolic events and early signs of allergic or hypersensitivity reactions, occurring between first infusion of IMP before the start of surgery and the Last Post-operative Day will be recorded.

All SAEs occurring after the first IMP infusion will be documented and reported for a patient throughout the duration of the patient's participation in the study or as required to meet local regulations. Also, any concomitant medications used to treat an SAE will be recorded.

6.1.3.1 Day 1

For subjects enrolled for surgical prevention, Day 1 is the day they undergo surgery and receive their first dose of *Octafibrin*.

The following surgery-related data will be recorded:

Pre-operative assessments

The following pre-operative assessments will be performed:

- Vital signs.
- Physical examination.
- Body weight (kg).

- Blood draw for:
 - fibrinogen plasma levels (local lab-activity; central lab-antigen and activity).
 - safety lab (local—haematology and clinical chemistry).
 - thrombogenicity.
 - retention plasma and serum samples for potential retesting.
- Urine (dip stick) or blood pregnancy test for all female subjects of childbearing potential.
- Location and type of surgery.
- Severity of surgery (minor/major).
- Expected duration of surgical procedure (start and end times, i.e., skin to skin).
- Expected blood loss for the procedure.
- Estimate of any blood/blood product transfusions needed during the surgery.
- Any planned ancillary therapy to be used during the surgery (e.g., antifibrinolytics, prepanned blood transfusions, etc.).

First infusion of Octafibrin

Following the pre-operative assessments and within 3 hours before the start of surgery, the subject may receive the first infusion of *Octafibrin* (see Section 5.4).

NOTE: If, in the investigator's judgement, there are no additional infusions of *Octafibrin* needed to prevent bleedings post surgery, the post-infusion assessments as detailed in the schedule for the **Last Post-Operative Day** should be performed instead.

Intra-operative assessments

The following assessments will be performed during or at the end of surgery:

- Blood draw for:
 - intra-operative fibrinogen plasma levels (local lab–activity; central lab–antigen and activity).
 - retention plasma samples for potential retesting.

Assessments at the end of surgery

- Blood draw for:
 - fibrinogen plasma levels (local lab-activity; central lab-antigen and activity).
 - thrombogenicity.
 - retention plasma samples for potential retesting.
- Actual duration of surgical procedure (start and end times, i.e., skin to skin).
- Details of surgery.
- Actual blood loss.
- Details on concomitantly administered products, including any blood/blood product transfusions but excluding drugs given for routine anaesthesia.
- Intra-operative efficacy assessment at the end of surgical procedure by the surgeon (see Section 7.2.2.3).
- AEs and concomitant medications.

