For each surgery that is treated as part of the study, within 3 hours prior to surgery, each subject will receive a loading infusion of *Octafibrin*.

Octafibrin will be individually dosed to achieve a recommended target fibrinogen plasma level dependent on the surgery type (minor or major).

- Patients undergoing **minor surgery** will be treated to achieve a recommended target fibrinogen plasma level of 100 mg/dL and an accepted lower limit of 80 mg/dL.
- Patients undergoing **major surgery** will be treated to achieve a recommended target fibrinogen plasma level of 150 mg/dL and an accepted lower limit of 130 mg/dL.

On each post-operative day, fibrinogen plasma levels will be measured daily to determine whether maintenance infusions of *Octafibrin* are needed:

- **Minor surgery** will be observed for at least 3 post-operative days.
- **Major surgery** will be observed for at least 7 post-operative days.

Maintenance infusions, as required:

- Additional infusions of *Octafibrin* **should** be administered if the actual fibrinogen plasma level measured on subsequent study days is below the accepted lower limit of the target level (80 mg/dL for minor surgery, 130 mg/dL for major bleeding).
- If the actual fibrinogen plasma level is above the accepted lower limit of the target level, *Octafibrin* **should not** be administered.

Name of Sponsor/Company:	
Octapharma AG	
Name of Investigational Product:	Protocol Identification Code:
Octafibrin	FORMA-02
Name of Active Ingredient:	Date of Final Protocol:
Fibrinogen	31-Oct-2014

Definition of minor and major surgery

Surgeries are defined as major, if any of the following criteria are met:

- Requiring general or spinal anaesthesia.
- Requiring opening into the great body cavities.
- In the course of which hazards of severe haemorrhage is possible.
- Requiring haemostatic therapy for at least 6 days.
- Orthopaedic interventions involving joints (ankle, knee, hip, wrist, elbow, shoulder).
- 3rd molar extraction or extraction of > 3 teeth.
- Surgeries/conditions in which the subject's life is at stake.

Characterisation of any other surgery not within these categories and considered major by the investigator will be discussed individually with the investigator.

All other surgeries are classified as minor. The classification is made prospectively.

Duration of Treatment:

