Octapharma AG	
Name of Investigational Product:	Protocol Identification Code:
Octafibrin	FORMA-02
Name of Active Ingredient:	Date of Final Protocol:
Fibrinogen	31-Oct-2014

Version 6.0

All SAEs occurring after the first IMP infusion will be documented and reported for a patient throughout the duration of the patient's participation in the study or as required to meet local regulations. Also, any concomitant medications used to treat an SAE will be recorded.

Dav 1

For subjects enrolled for surgical prevention, Day 1 is the day they undergo surgery and receive their first dose of *Octafibrin* in this study. The following surgery-related data will be recorded:

Pre-operative assessments

The following data will be recorded before surgery:

- Vital signs.
- Physical examination.
- Body weight (kg).
- Blood draw for:
 - fibringen plasma levels (local lab-activity; central lab-antigen and activity)
 - safety lab (local-haematology and clinical chemistry).
 - thrombogenicity.
 - retention plasma and serum samples for potential retesting.
- Urine (dip stick) or blood pregnancy test for all female subjects of childbearing potential.
- Location and type of surgery.
- Severity of surgery (minor/major).
- Expected duration of surgical procedure (start and end times, i.e., skin to skin).
- Expected blood loss for the procedure.
- Estimate of any blood/blood product transfusions needed during the surgery.
- Any planned ancillary therapy to be used during the surgery (e.g., antifibrinolytics, prepanned blood transfusions, etc.).

First infusion of Octafibrin

Following the pre-operative assessments and within 3 hours before the start of surgery, the subject may receive the first infusion of Octafibrin.

NOTE: If, in the investigator's judgement, there are no additional infusions of *Octafibrin* needed to prevent bleedings post surgery, the post-infusion assessments as detailed in the schedule for the Last Post-Operative Day should be performed instead.

Name of Sponsor/Company:	
Octapharma AG	
Name of Investigational Product: Protocol Identification Code:	
Octafibrin	FORMA-02
Name of Active Ingredient:	Date of Final Protocol:
Fibrinogen	31-Oct-2014

Intra-operative assessments

The following data will be recorded during and at the end of surgery:

- Blood draw for:
 - intra-operative fibrinogen plasma levels (local lab–activity; central lab–antigen and activity).
 - retention plasma samples for potential retesting.

Assessments at the end of surgery

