3.2.2 Surgical Prophylaxis

Subjects planning to undergo elective surgery may also be enrolled in the study.

Within 3 hours prior to surgery, each patient will receive a loading infusion of *Octafibrin* to achieve a recommended fibrinogen plasma level of 100 mg/dL for minor surgeries and 150 mg/dL for major surgeries.

Each subject's **surgical observation period** starts with the first dose of *Octafibrin* administered prior to elective surgery (Day 1) and, depending on the severity of the event, will last at least 3 post-operative days for minor and 7 post-operative days for major surgeries or until the day of the last post-operative infusion, whichever comes last.

On each post-operative day, fibrinogen plasma levels will be measured daily (i.e., at least 3 post-operative days for minor and 7 post-operative days for major surgeries) to determine whether additional infusions of *Octafibrin* are needed.

- Additional infusions of Octafibrin should be administered if the actual fibrinogen plasma level measured on subsequent days is below the accepted lower limit of the target level (80 mg/dL for minor surgeries, 130 mg/dL for major surgery).
- If the fibrinogen plasma level is greater than or equal to the accepted lower limit of the target fibrinogen plasma level, *Octafibrin* **should not** be administered.

The actual treatment duration will be determined by the investigator based on his/her judgement of the subject's condition.

All AEs, including thromboembolic events and early signs of allergic or hypersensitivity reactions, occurring between first infusion of IMP before the start of surgery and the Last Post-Operative Day will be recorded.

All SAEs occurring after the first IMP infusion will be documented and reported for a patient throughout the duration of the patient's participation in the study or as required to meet local regulations. Also, any concomitant medications used to treat an SAE will be recorded.

At the end of the study (i.e., when the 24th patient has had at least one treated bleeding episode), all patients will be asked to return for a Study Completion Visit.

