5.4.3 Dosing for Surgery

For each surgery that is treated as part of the study, within 3 hours prior to surgery, subjects will receive a loading infusion of *Octafibrin*.

Octafibrin will be individually dosed to achieve a recommended target fibrinogen plasma level dependent on the surgery type (minor or major).

- Patients undergoing **minor surgery** will be treated to achieve a recommended target fibringen plasma level of 100 mg/dL and an accepted lower limit of 80 mg/dL.
- Patients undergoing **major surgery** will be treated to achieve a recommended target fibrinogen plasma level of 150 mg/dL and an accepted lower limit of 130 mg/dL.

On each post-operative day, fibrinogen plasma levels will be measured daily to determine whether maintenance infusions of *Octafibrin* are needed.

- Minor surgery will be observed for at least 3 post-operative days.
- Major surgery will be observed for at least 7 post-operative days.

Maintenance infusions, as required:

- Additional infusions of *Octafibrin* **should** be administered if the actual fibrinogen plasma level measured on subsequent study days is below the accepted lower limit of the target level (80 mg/dL for minor surgery, 130 mg/dL for major bleeding).
- If the actual fibrinogen plasma level is above the accepted lower limit of the target level, *Octafibrin* **should not** be administered.

Definition of minor and major surgery

Surgeries are defined as major, if any of the following criteria are met:

- Requiring general or spinal anaesthesia.
- Requiring opening into the great body cavities.
- In the course of which hazards of severe haemorrhage is possible.
- Requiring haemostatic therapy for at least 6 days.
- Orthopaedic interventions involving joints (ankle, knee, hip, wrist, elbow, shoulder).
- 3rd molar extraction or extraction of > 3 teeth.
- Surgeries/conditions in which the subject's life is at stake.

Characterisation of any other surgery not within these categories and considered major by the investigator will be discussed individually with the investigator.

All other surgeries are classified as minor.

The classification is made prospectively.

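### The protocol says both that surgical subjects will and that they may receive Octafibrin before surgery, and the analysis would not separate a surgery done without it

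*Protocol*

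**What the plan says.** Three places in the protocol state the pre-operative infusion as something that happens to everyone. The synopsis text on dosing for surgery has "within 3 hours prior to surgery, each subject will receive a loading infusion of" Octafibrin. Section 3.2.2 has "Within 3 hours prior to surgery, each patient will receive a loading infusion of" Octafibrin. Section 5.4.3 has "within 3 hours prior to surgery, subjects will receive a loading infusion of" Octafibrin.

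Two places use permissive wording. Section 6.1.3.1 has "within 3 hours before the start of surgery, the subject may receive the first infusion of" Octafibrin, followed by a cross-reference to Section 5.4. The synopsis copy of that step has "within 3 hours before the start of surgery, the subject may receive the first infusion of Octafibrin", with no cross-reference.

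The opening of Section 6.1.3, also repeated in the synopsis, adds discretion. It says that the product "will be given prior to surgery as well as during and after surgery based on the physician's judgement, the patient's history"; how severe the operation is comes as a third consideration.

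Other parts presuppose a pre-operative dose. Section 6.1.3.1 itself says "Day 1 is the day they undergo surgery and receive their first dose of" Octafibrin. Sections 3.1.2, 3.2.2 and 6.2.2 start the surgical observation period at the dose given before elective surgery. The surgical flow charts in the protocol and in SAP Section 4.5.2 show the infusion before the start of surgery with no condition attached.

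**The concern.** A site reading the dosing sections and a site reading the procedures section could reach different conclusions about whether the pre-operative infusion is required. That matters for subjects, because inclusion requires historical fibrinogen activity below 50 mg/dL or below detection, while the surgical targets are 100 or 150 mg/dL. Treatment instructions on this point should not conflict.

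It also matters for interpretation. Showing efficacy in preventing bleeding during and after surgery is a stated secondary objective. If an operation went ahead without product beforehand, a good intra-operative rating would say little about Octafibrin, yet it would enter the same summary as the others.

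**Working it through.** No power or sample-size figure bears on this point, so the check is a comparison of texts.

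**Step 1. Is the conflict real?**

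| Place in the protocol | Verb | Condition attached |
|---|---|---|
| Synopsis, dosing for surgery | will | none |
| Section 3.2.2 | will | none |
| Section 5.4.3 | will | none |
| Section 6.1.3, opening (and synopsis copy) | will | physician's judgement, history, severity |
| Section 6.1.3.1 | may | points to Section 5.4 |
| Synopsis, Day 1 for surgery | may | none |

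The synopsis disagrees with itself, and so does the body. The matching step for bleeding, Section 6.1.2.1, uses *will* for the first infusion. So *may* is not simply the protocol's usual phrasing for this step.

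**Step 2. Which reading does the rest of the plan assume?** The Day 1 definition and the observation period are both tied to a dose on the day of, or before, surgery. In both flow charts only the intra-operative infusion carries the footnote that makes it discretionary. The post-operative infusions depend on the measured fibrinogen level, and the pre-operative one has no footnote. The structure of the plan therefore assumes a pre-operative dose.

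**Step 3. Would the analysis separate a surgery whose first infusion came during or after the operation?**

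- Protocol Section 9.3.2 asks for a need for at least one infusion between the day of surgery and the efficacy assessment. It does not say the infusion must be pre-operative. SAP Section 4.4.2 drops the time window as well.
- The per-protocol rule (Protocol 9.3.3, SAP 4.4.3) requires at least 90% of the planned dose in the first infusion, without saying when that infusion falls.
- The top three intra-operative categories in Protocol Table 3 compare blood loss with what is expected under normal haemostasis. They do not depend on product having been given.
- In Protocol Table 6, an intra-operative rating of excellent gives success when the post-operative rating is excellent, good or moderate.
- SAP Section 8.3.5 covers unexpected blood loss from surgical complications but has no rule for a missing pre-operative infusion.

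So such a case would stay in the summary unmarked. A subject never infused at all would be outside both the safety population and the full analysis set.

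**Step 4. Size.** The plan commits to at least 4 surgeries, so one surgery is at most 1/4 = 25% of the planned minimum. That is true of any single surgery, whatever happens in it. It does not estimate how often the infusion would be omitted, and the documents give no figure for that.

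**The case against.** The strongest reply is that *may* is loose drafting. The sentence in Section 6.1.3.1 points to Section 5.4, which says *will*. It can be read as opening a time window once the pre-operative assessments are done. The authors had a marker for discretionary infusions and did not put it on the pre-operative one. Nothing ranks the procedures section above the dosing section. This reply stands as far as it goes: it shows the probable intent. It does not remove the conflict, because the synopsis copy has no cross-reference, the opening of Section 6.1.3 invokes physician's judgement, and SAP Section 4.5.3 sends its reader to protocol Section 6.1 for procedures.

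There are also safeguards. Pre-, intra- and post-operative doses are recorded (Protocol 7.2.2.3), and the adjudication committee reviews the surgical case along with the ratings. An operation without a pre-operative dose would probably be noticed. But no rule says how it should then be reported.

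A reader might go further and infer that sites are free to operate with or without the infusion, so that the surgical endpoint covers two different treatments. The documents do not support that: no section describes surgery without a pre-operative dose. A reader might also infer that adverse event collection would have no defined start. That does not hold either. Protocol Section 7.4 starts recording at the first Octafibrin infusion, whenever it is given. Only the observation-period wording and the adverse event notes in Sections 3.2.2 and 6.1.3 (with its synopsis copy) assume a pre-operative dose.

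**Conclusion.** The inconsistency is established from the text and should be corrected. Its consequences are limited. Surgery without a pre-operative infusion is something the *may* wording could allow if read alone, not an established feature of the trial. The endpoint concerned is secondary and descriptive, with no hypothesis test and a minimum of 4 surgeries. The primary bleeding endpoint is not affected. What remains is the need for one consistent treatment instruction to sites, and a small gap in how an exceptional surgery would be reported.

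This rests on protocol Version 6.0. The SAP is written against Version 7.0 of 08-July-2016, which is not among the documents, so whether the *may* wording survives there could not be checked.

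**What to change.** In the protocol, reconcile the Day 1 step in Section 6.1.3.1, the opening of Section 6.1.3, and the synopsis copies of both with the synopsis dosing text and Sections 3.2.2 and 5.4.3, so that one rule on the pre-operative infusion applies throughout. Which rule is a clinical decision for the sponsor. First check whether Version 7.0 has already done this.

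In SAP Section 8.3.5, add one sentence: all surgeries stay in the analysis, and any done without a pre-operative infusion is listed or flagged. Limiting the intra-operative analysis to surgeries that received the infusion would select by treatment received, which sits badly with the stated intention-to-treat principle and presumes an answer to the clinical question.

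The cost is a wording correction, one SAP sentence and one listing. No new data are needed, because doses are already recorded. If an amendment is required, Section 10.4 calls for ethics committee approval of changes that could affect subject safety, and this may be one.
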